### **2.2 Study Endpoints**

#### **2.2.1 Efficacy Endpoints**

The primary efficacy endpoint is:

- The mean change from baseline in the total CAPS-5 score after 12 weeks of treatment evaluated at Visit 6. The primary efficacy comparison will be the change from baseline in total CAPS-5 score for the 5.6 mg treatment arm compared to placebo.

Key secondary efficacy endpoints for labeling purposes include:

- Clinical Global Impression – Improvement (CGI-I) score analyzed as a continuous variable (1-7) after 12 weeks of treatment comparing the 5.6 mg treatment arm to placebo.
- Change from baseline in Sheehan Disability Scale (SDS) total score after 12 weeks of treatment comparing the 5.6 mg treatment arm to placebo.

Other secondary efficacy endpoints include:

- Change from baseline in participants' quality of sleep using the Patient-Reported Outcome Measurement Information System (PROMIS) Sleep Disturbance scale after 12 weeks of treatment.
- Change from baseline in the disruption of work/school activities assessed using the SDS after 12 weeks of treatment.

- Change from baseline in disruption of social life/ leisure activities assessed using the SDS after 12 weeks of treatment.
- Change from baseline in the disruption of family life/home responsibilities assessed using the SDS after 12 weeks of treatment.
- Change from baseline in CAPS-5 Arousal and Reactivity (Criterion E) score after 12 weeks of treatment.
- Change from baseline in CAPS-5 Intrusion symptoms (Criterion B) score after 12 weeks of treatment.
- Change from baseline in CAPS-5 Persistent Avoidance (Criterion C) score after 12 weeks of treatment.
- Change from baseline in CAPS-5 Negative Cognition and Mood (Criterion D) score after 12 weeks of treatment.
- Change from baseline in CAPS-5 Sleep Disturbance (item E-6) score after 12 weeks of treatment.
- Change from baseline in CAPS-5 Exaggerated Startle (item E-4) score after 12 weeks of treatment.
- Patient Global Impression of Change Scale (PGIC) score after 12 weeks of treatment.
- Proportion of participants with a PGIC score of “much improved” or “very much improved” after 12 weeks of treatment.
- Proportion of CGI-I Responders, defined as a CGI-I score of 2 (“much improved”) or 1 (“very much improved”), after 12 weeks of treatment.
- Proportion of participants with a Total CAPS-5 score of 0 –10 (asymptomatic/few symptoms) after 12 weeks of treatment.
- Proportion of participants with a Total CAPS-5 score of 0-22 (asymptomatic or mild PTSD/subthreshold) after 12 weeks of treatment.
- Proportion of participants with Response, defined as a  $\geq 10$ -point improvement from baseline in Total CAPS-5 score after 12 weeks of treatment.
- Proportion of participants with Loss of Diagnosis, defined as Response AND no longer meeting DSM-5 symptom criteria in any one or more of the four clusters (B, C, D, E) after 12 weeks of treatment.
- Proportion of participants in Remission, defined as Loss of Diagnosis AND Total CAPS-5 score  $\leq 10$  after 12 weeks of treatment.
- Proportion of participants achieving sustained Remission, defined as Loss of Diagnosis AND Total CAPS-5 score  $\leq 10$  after both 8 weeks AND 12 weeks of treatment.

- Proportion of participants with a  $\geq 50\%$  improvement from baseline in Total CAPS-5 score after 12 weeks of treatment.
- Change from baseline in Beck Depression Inventory–II (BDI-II) score after 12 weeks of treatment.
- Change from baseline in CAPS-5 Reckless or Self-Destructive Behavior (item E-2) score after 12 weeks of treatment.

### **2.2.2 Exploratory Efficacy Endpoints**

Exploratory efficacy endpoints include:

- Change from baseline in the CAPS-5 item for depersonalization (CAPS-5 item 29) after 12 weeks of treatment
- Change from baseline in the CAPS-5 item for derealization (CAPS-5 item 30) after 12 weeks of treatment.

### **2.2.3 Safety Endpoints**

Safety will be assessed by:

- Adverse events (AE) and serious AEs (SAEs) throughout the entire duration of the study, including detailed assessment of AEs involving the oral cavity.
- Changes from baseline in clinical laboratory test results.
- Changes from baseline in vital signs and weight.
- Change from baseline in BDI-II.
- Changes from baseline in suicidal ideation or behavior as reported on the Columbia Suicide Severity Rating Scale (C-SSRS).
- Changes from baseline in participant-rated Changes in Sexual Functioning Questionnaire Short-Form (CSFQ-14).
- Changes from baseline in participant-rated morning sedation as assessed by the Morning Treatment-Related Sedation Score (MTRSS).

### **3. OVERALL STUDY DESIGN AND PLAN**

This is a Phase 3, 12-week, randomized, multicenter, double-blind, placebo-controlled, fixed dose study that will investigate the efficacy and safety of TNX-102 SL 5.6 mg taken daily at bedtime for the management of military-related PTSD. This study is to be conducted at approximately 45 investigational sites in the United States.

The total duration of this study over 6 visits will be approximately 13-17 weeks, with 12 weeks of treatment duration and a variable length of screening. This study will consist of a Screening visit (Visit 1, Days -35 to -7), Randomization visit (Visit 2, Day 0), telephone visit (Visit 3, Week 2) and three monthly in-clinic visits (Visits 4, 5 and 6 at Weeks 4, 8, and 12).

Eligible participants who provide written informed consent to participate will have study assessments performed at Screening, including counseling regarding any required washout and instructions to refrain from use of excluded medications throughout the study.

The length of the pre-randomization screening period is variable (7 to 35 days) in order to accomplish wash-out of previous medications, where appropriate, and allow for return of clinical laboratory results necessary to confirm eligibility. At Visit 2, participants will return to the site for additional baseline assessments and randomization (Day 0), when, if they meet all study randomization criteria, they will be randomly assigned in a 1:1 ratio to receive placebo or TNX-102 SL 5.6 mg. A dynamic randomization procedure will be employed at Visit 2 to minimize trial-wide imbalances between the treatment groups for site, sex, current tobacco/nicotine use (yes/no) and presence (yes/no) of current Major Depressive Episode (MDE) based on the Mini International Neuropsychiatric Interview, Version 7.0.2 (MINI 7.0.2) conducted at Visit 1.

Participants will take the study drug sublingually daily at bedtime, starting on the day that they are randomized and continuing for 12 weeks. Participants will return to the study center for safety and efficacy assessments at Weeks 4, 8, and 12 (or early termination [ET]).

#### **3.1 Selection of Study Population**

For a complete list of inclusion and exclusion criteria please refer to the initial protocol issued 06 October 2016, Amendment 1, dated 03 February 2017, Amendment 2, dated 28 March 2017 and Amendment 3, dated 18 May 2018.

#### **3.2 Method of Treatment Assignment and Randomization**

Once all pre-randomization assessments have been completed, only those participants who meet all of the following randomization criteria will be eligible to continue:

1. Participant continues to meet all inclusion and exclusion criteria, including urine and blood test results, and
2. Visit 2 total CAPS-5 score  $\geq$  33 (“Symptom Severity” version using 1-week recall), and

3. At Visit 2, participant is not severely depressed (based on the investigator's judgment and Visit 2 C-SSRS, CAPS-5, and BDI-II, and considering the pre-randomization collaborative review by the investigator and medical monitor(s) of the participant's Visit 1 psychiatric history, presenting symptomatology, MINI 7.0.2, C-SSRS, CAPS-5, and BDI-II assessments).
4. No active suicidal intent or plan, based on Investigator's judgment, and Visit 2 C-SSRS responses (e.g., no C-SSRS Type 4-5 ideation or suicidal behavior since Visit 1).

If the participant meets all study randomization criteria, they will be randomly assigned in a 1:1 ratio to receive placebo or TNX-102 SL 5.6 mg for 12 weeks. A dynamic randomization procedure will be employed at Visit 2 to minimize trial-wide imbalances between the treatment groups for site, sex, current tobacco/nicotine use (yes/no) and presence (yes/no) of current MDE based on the MINI conducted at Visit 1.

Treatment A: 2 x TNX-102 SL 2.8 mg tablets ("TNX-102 SL") to be taken sublingually once daily at bedtime.

Treatment B: 2 x placebo tablets ("placebo") to be taken sublingually once daily at bedtime.

### **3.3 Treatment Blinding**

This is a double-blind study. Unless otherwise specified, all study personnel are to remain blinded to study drug. Treatment assignments will not be revealed until all participants have completed the study and the database has been finalized and closed. Completion of study may occur due to early stop based on interim analysis results (either for futility or efficacy); initial results may be released at that time, followed by a full final analysis for the clinical study report.

If AEs occur that are considered to be intolerable, the investigator must decide whether it is necessary for the participant to discontinue study drug; however, the investigator should not be unblinded unless it is imperative for the participant's overall safety to determine whether the participant received active study drug (e.g., in the event of overdose of investigational product).

### **3.4 Minimization of Missing Data / Dropout rate**

It is important to avoid missing data from clinical trials. The following strategies are designed to minimize drop-outs and missing data in this study:

- Providing participants with greater background on the nature of placebo-controlled clinical trials and explaining that completing this study, regardless of the participant's level of treatment response, is essential to understanding whether TNX-102 SL may be helpful to others in the treatment of PTSD. Sites will explain that the study is not designed to benefit the individual

participant but, rather, can only provide useful information for future therapeutics.

- Minimizing the burden on participants, with visits scheduled generally every 4 weeks (with reasonable visit window flexibility). Clinical site personnel will also receive guidance regarding the special considerations necessary when dealing with participants with military PTSD.
- Training of site personnel on the importance of minimizing missing data.
- Providing payment for participants' time and effort at clinic visits, based on the duration of assessments and as approved by the Institutional Review Board. Reimbursement for travel expenses to and from the clinic sites may also be provided to further minimize the financial burden of participating in the study.
- Utilizing repeated assessments of outcome measures and analytical approaches that most appropriately compensate for missing data.
- Offering open-label continuation trial(s) for those successfully completing the double-blinded study and for randomized participants who have not yet completed the study if the study is stopped early for success.

## **4. ANALYSIS AND REPORTING**

### **4.1 Interim Analysis**

An interim analysis will be performed by a statistical group independent of both the sponsor and contract research organization (CRO) performing the final analysis when approximately 50% of the initially planned enrollment is evaluable for efficacy assessments. An IDMC will review the data and recommend to the Sponsor to increase the sample size by a fixed amount, keep the current sample size and continue, stop the study early for success, or stop the study early for futility. The ISAP, the IDMC charter and the Adaptive Study Simulation Report are being submitted together with this version of the SAP to the FDA.

The interim analysis will be conducted approximately 12 weeks after randomization of approximately 275 participants, i.e. when approximately 50% of the initially planned participant enrollment (550) is evaluable for efficacy assessments. These approximately 275 participants of the interim analysis will define the Early Stop Efficacy Population (see [Section 6](#)).

In case the study is stopped early for success, eligible participants who are not included in the early stop efficacy population will be immediately transitioned to an open label extension safety study.

In case the study is stopped early for futility, participants will be managed according to a study termination plan.

In the case of an early stop for futility or efficacy, initial results may be released prior to full database lock; however, CSR results will be based on the final analysis described below.

### **4.2 Final Analysis**

All final, planned analyses will be performed after the last participant has completed all study assessments, all relevant study data have been processed and integrated into the analysis database, and the database has been locked. As described above, in the event of the interim analysis triggering an early stop for success, only those participants who are part of the early stop efficacy population will be analyzed, and eligible participants who are not included in the early stop efficacy population will be immediately transitioned to an open label extension safety study. Efficacy assessment will not be done prior to transition to TNX-CY-P306.

Any post-hoc, exploratory analyses completed to support planned study analysis, which were not identified in this SAP, will be documented and reported in appendices to the CSR. Any results from these unplanned analyses (post-hoc) will also be clearly identified in the text of the CSR.

## 5. SAMPLE SIZE DETERMINATION

The study is planned to enroll approximately 550 participants total in a 1:1 randomization, that is, 275 participants in each of the placebo and TNX-102 SL 5.6 mg groups.

The interim analysis will re-evaluate these assumptions and the IDMC may recommend a sample size increase.

## 6. ANALYSIS POPULATIONS

The following analysis populations are planned for this study:

- **Safety Population (SAFETY):** All participants who receive at least 1 dose of study drug. Participants who are issued study drug, but return 100% of it (i.e., none consumed) will be excluded from the safety population; likewise participants that have no follow up following receipt of study drug to indicate they took drug are excluded. All safety analyses and demographic/baseline characterization will be performed using this population, analyzed as treated; participants will be summarized under TNX-102 SL 5.6 mg if they were issued it at any visit (including participants that are rolled over to open-label TNX-102 SL 5.6 mg in the case of an early stop recommended by the IDMC during the planned interim analysis).
- **Modified Intention-to-Treat Population (mITT):** All randomized participants who have at least a baseline and one post-baseline CAPS-5 assessment. This is the primary population for efficacy analyses and participants will be analyzed based on their randomized treatment.
- **Early Stop Safety Population (SAFETY):** This population is identical to the safety population but is limited to only the participants that are part of the interim analysis, (i.e. participants that are ongoing at the time of early stop are excluded). In the case of an early stop, safety results will be analyzed on both safety populations. Should the study continue to full enrollment (or full enrollment on an increased sample size), this population will not be utilized.
- **Early Stop Efficacy Population (mITT):** This population will be limited to those participants who are part of the interim analysis, i.e., among the approximately 275 patients defined as the population upon which the predefined interim analysis efficacy assessments will be conducted. Only those participants who have a baseline and at least one post-baseline CAPS-5 assessment will be evaluated for purposes of the interim analysis. Participants will be analyzed based on their randomized treatment. The dataset for this population will be defined by the completion or early termination of the last participant among this cohort.

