## **7. GENERAL ISSUES FOR STATISTICAL ANALYSIS**

### **7.1 General Statistical Methodology**

Descriptive summaries will be provided where appropriate for each of the primary and secondary variables. In general, tables will summarize data by treatment group and visit.

Baseline characteristic and safety tables will be completed for the Safety Population unless otherwise specified. Efficacy tables will be presented for the mITT Population.

Continuous, quantitative, variable summaries will include the number of participants (N) with non-missing values, mean, standard deviation (SD), median, minimum, and maximum.

Categorical, qualitative, variable summaries will include the frequency and percentage of participants who are in the particular category. In general, the denominator for the percentage calculation will be based upon the total number of participants in the study population for the treatment group unless otherwise specified.

Baseline values are defined as the last non-missing measurement prior to the first dose of study drug. Change from baseline will be defined as the post-baseline visit value minus the baseline value.

ET participants will only be followed if required to monitor an on-going adverse event or other condition.

Participants are not supposed to change study sites; however, should this be necessary to allow a participant to continue in the study, participants will be analyzed under the site where they were initially enrolled.

Study day after first dose is defined as assessment date – first dose date +1. Dates prior to first dose are defined as assessment date – first dose date. Note that the protocol refers to “Day 0”; for the purposes of the datasets and analyses, this would appear as day 1.

All analyses will be performed using Statistical Analysis System (SAS®) Software version 9.3 or later.

Alpha levels are discussed in [Section 7.1.1.2](#) below; unless otherwise noted, 95% confidence intervals will be presented for statistical tests.

Presence of current tobacco/nicotine use and MDE is recorded first in the Interactive Web Response System (IWRS) during screening for purposes of randomization stratification and, after randomization, transcribed into the electronic data capture (EDC) system (as part of substance use history and the results for the MINI). The source for tobacco/nicotine use MDE in all analyses and statistical models will be the EDC data and not the IWRS.

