#### 7.3.1 Adverse Event and Prior/Concomitant Medication handling conventions

To handle missing or partial AE and prior/concomitant medication dates, the following rules will be applied.

For partial start dates:

1. If the year is unknown, then do not impute the date but assign a missing value.
2. If the month is unknown, then:

- a. If the year matches the year of the first dose date, then impute the month and day of the first dose date.
  - b. Otherwise, assign “January.”
3. If the day is unknown, then:
- a. If the month and year match the month and year of the first dose date, then impute the day of the first dose date.
  - b. Otherwise, assign “01.”

For partial end dates:

1. If the year is unknown, then do not impute the date but assign a missing value.
2. If the month is unknown, then assign “December.”
3. If the day is unknown, then assign the last day of the month.

Adverse events are categorized as either pre-treatment adverse events or treatment-emergent adverse events based on the response to the CRF question “Did the AE start prior to the first dose?”

After implementing the rules above, to determine whether medications with missing start or stop dates are prior or concomitant medications, the following strategy will be used:

1. If the start date and stop date are both missing, then the most conservative approach is taken and the medication is considered to be a concomitant medication.
2. If the start date is missing but the stop date is not missing and is after the day of first study dose administration, then the most conservative approach is taken and the medication is considered to be concomitant.
3. If the start date is missing but the stop date is not missing and is on or before the day of first study dose and after the date of signed informed consent, then the medication is considered to be a prior medication.
4. If the start date is not missing but the stop date is missing, then the most conservative approach is taken and medication is considered to be concomitant.

The missing severity of an AE will be imputed to “severe”; the missing relationship to study drug of an AE will be imputed to “related”.

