## **10. SAFETY AND TOLERABILITY ANALYSIS**

The safety analysis will be run on the Safety population. The analysis of safety assessments in this study will include summaries of the following safety and tolerability data collected for each participant:

- Adverse Events
- Clinical Laboratory Investigations
- C-SSRS
- Vital Signs
- Visual Examinations of Oral Cavity
- Electrocardiogram (ECG) Parameters (Obtained at Screening only)
- Assessment of Morning Sedation (via MTRSS)
- Changes from baseline in participant-rated CSFQ-14
- BDI-II

Summaries of continuous parameters will include raw values and change from baseline, as appropriate. Listings of safety data will also be presented.

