### **10.1 Adverse Events**

All AEs, treatment-emergent adverse events (TEAEs), and SAEs will be coded using MedDRA, version 19.0.

TEAEs are defined as either new onset AEs with an onset at the time of or following the start of treatment through ten days after the last dose of study medication, or a recurrence of an AE (or medical history) present prior to randomization but increasing in severity, frequency or relationship at the time of or following the start of treatment

An AE summary table will be presented for the following:

- TEAEs by severity
- TEAEs leading to study drug discontinuation
- TEAEs by relationship
- SAEs

Summaries of incidence rates (frequencies and percentages) of individual AEs by MedDRA SOC and preferred term will be prepared. Such summaries will be displayed for all TEAEs, TEAEs by maximum severity, and TEAEs by strongest relationship to study drug.

Each participant will be counted only once within each summation level (SOC; preferred term). If a participant experiences more than one TEAE within each summation level only, the TEAE with the strongest relationship or the maximum severity, as appropriate, will be included in the summaries of relationship and severity.

Adverse events of special interest pertaining to abuse potential (as defined in the January 2017 Assessment of Abuse Potential for Drugs – Guidance for Industry) will be analyzed separately by treatment group, SOC and preferred term, and displayed in tabular format.

In the AE data listings, all AEs will be displayed. AEs that are treatment-emergent will be flagged.

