### 11.2 Exposure and Compliance

The treatment duration will be calculated as (number of days=last dose date - first dose date+1) and summarized. Participants that are lost to follow up or have a missing last dose date will be assigned a last dose date of the day before the last attended clinic visit for analysis purposes.

All pill count shortage (negative pill count) of greater than 4 doses (8 tablets) per 4-week assessment period and/or any between-visit compliance <70% will be considered protocol deviations, and the reason for the pill count discrepancy will be discussed with the participant and documented in the CRF to ensure that any cases of potential abuse or misuse are identified. Participants with more than one significant incidence of negative pill count discrepancy during the double-blind phase of the study will be closely monitored by the investigator.

Exposure will be measured using the last date of treatment and first date of treatment. Total exposure will be defined as the last date of treatment minus the first date of treatment plus one. The number of participants with total exposure by visit weeks ( $\leq 4$  weeks (study day 0 to 28), 4 to  $\leq 8$  (study day 29 to 56), 8 to  $\leq 12$  (study day 57 to 84) and  $> 12$  weeks (study day  $\geq 85$ )) will be presented. Additionally, exposure days, defined as the total number of tablets taken divided by 2 (and rounded up to the nearest whole number), will be summarized.

Compliance will similarly be summarized across all study visits for each treatment arm. Study drug compliance as a percentage will be defined as the number of pills taken by the participant divided by the total number of pills that the participant was assigned to take multiplied by 100.

For calculating the compliance and exposure days, the following convention will be applied: for periods where drug is issued, but the participant does not return any bottles or tablets, or the participant misses the visit entirely, that period will not contribute to the compliance or exposure calculation unless the bottles are returned at a later visit.

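### After an early stop for success, placebo participants who roll over to open-label drug are counted under TNX-102 SL in the Safety Population, with no visible data cut at the first open-label dose

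*SAP*

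**What the plan says.** SAP 6 defines the Safety Population as treated. A participant is placed under TNX-102 SL 5.6 mg "if they were issued it at any visit (including participants that are rolled over to open-label TNX-102 SL 5.6 mg" after an early stop recommended by the IDMC. Protocol 13.1 has a similar as-treated rule, based on the largest dose dispensed at any time, but does not mention rollover.

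This population is the default for safety output. SAP 7.1 states "Baseline characteristic and safety tables will be completed for the Safety Population unless otherwise specified", and SAP 10 states "The safety analysis will be run on the Safety population".

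SAP 6 also defines an Early Stop Safety Population that leaves out participants still ongoing at the stop, and adds: "In the case of an early stop, safety results will be analyzed on both safety populations".

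Rollover is open to both arms. Protocol 13.6 and SAP 4.1 and 9.1.1 offer or give ongoing randomized participants an immediate move to the open-label study TNX-CY-P306 if the trial stops for success.

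The rules that could separate placebo time from open-label time are these:
- Baseline (SAP 7.1) is the last value before the first dose of study drug.
- SAP 7.3.1: "Adverse events are categorized as either pre-treatment adverse events or treatment-emergent adverse events based on the response to the CRF question" on whether the event began before the first dose.
- SAP 10.1 counts new events with onset at or "following the start of treatment through ten days after the last dose of study medication".
- SAP 11.2: "Total exposure will be defined as the last date of treatment minus the first date of treatment plus one".

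**The concern.** An as-treated rule normally handles dispensing errors within the blinded period. This one relabels a completed placebo period because of what the participant received afterwards. Allocation is 1:1, so about half of those who roll over will have spent their double-blind time on placebo. Their data from that time enter the drug column and leave the placebo column, so the table is no longer a valid double-blind comparison.

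An early stop for success is one of the planned IDMC outcomes, and SAP 1 describes the trial as a pivotal efficacy study. In that outcome, one safety table mixes placebo time into the drug column and the other drops everyone ongoing. No table in the documents available shows all double-blind safety data by the treatment received in that period.

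A smaller, separate gap concerns the ten-day window for treatment-emergent events, which can overlap open-label dosing. This applies to early-stop rollovers. It can also apply in any branch to completers who enter an extension within ten days, since SAP 3.4 includes "Offering open-label continuation trial(s) for those successfully completing the double-blinded study". The SAP does not say which study counts such an event.

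**Working it through.** **Text check.** For a placebo participant who rolls over, baseline precedes the first placebo dose. Events are only pre-treatment or treatment-emergent relative to that dose. The event window and exposure run to a last dose, with no switch of treatment label. No re-baseline, period-specific treatment assignment or cut at the first open-label dose appears in either document.

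**The plan's own figure.** Interim cohort: 0.5 × 550 = 275, as SAP 4.1 states.

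**Illustration of size.** The documents give neither the number ongoing at the stop, nor rollover uptake, nor event rates, so what follows rests on stated assumptions.

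1. *Accrual.* The Protocol synopsis dates run from February 2017 to January 2019. Less 12 weeks of treatment, that is about 20 months: 550/20 = 27.5 per month.
2. *Ongoing at the cut-off.* The interim comes about 12 weeks after the 275th randomization (SAP 4.1). In that time 27.5 × 84/30.4 = 76.0 more are randomized. Each arm then has (275 + 76.0)/2 = 175.5.
3. *Placebo participants moved.* High case (no dropout, full uptake): 76.0/2 = 38.0. Low case (20% dropout, 50% uptake): 76.0 × 0.8 × 0.5/2 = 15.2.
4. *Share of the drug column.* High: 38.0/(175.5 + 38.0) = 17.8%. Low: 15.2/190.7 = 8.0%. The placebo column loses 38.0/175.5 = 21.6% or 15.2/175.5 = 8.7% of its members.
5. *Dilution, double-blind events only, equal risk in moved and unmoved placebo participants.* With m moved and n per arm, the observed difference is n/(n + m) times the true one. Kept: 82.2% (high), 92.0% (low).

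**Variations**

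| Assumption changed | Share of drug column | True excess kept |
|---|---|---|
| 8 weeks from cut-off to decision, enrollment continuing (+27.5 × 56/30.4 = 50.7 randomized; arm 200.8) | 7.0–15.9% | 84.1–93.0% |
| Accrual over 15 months (stated 1.5 years less 12 weeks; 101.3 randomized; arm 188.2; 20.3–50.7 moved) | 9.7–21.2% | 78.8–90.3% (100% minus the share) |

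**Incomplete follow-up.** Those moved have been followed for less than 12 weeks. Suppose ongoing participants carry half the 12-week risk, and true risks are 20% on drug and 10% on placebo.
- High: drug column (137.5 × 0.20 + 38 × 0.10 + 38 × 0.05)/213.5 = 15.55%; placebo column 10.0%. The difference is 5.55 points, against 8.92 as randomized: 62.2% kept.
- Low: 7.68 against 9.13 points: 84.1% kept.
- With 10% in both arms and no true difference, the drug column looks lower by 1.78 points (high) or 0.72 points (low).

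**If open-label events are also counted.** Take 20% versus 10% again, full risk in each period and independent periods. Each mover has risk 1 − 0.9 × 0.8 = 0.28.
- High: (175.5 × 0.20 + 38 × 0.28)/213.5 = 21.4%, a difference of 11.4 points against a true 10.
- Low: (175.5 × 0.20 + 15.2 × 0.28)/190.7 = 20.6%, a difference of 10.6 points.

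The direction of the error therefore depends on a rule the SAP does not give.

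**The case against.** The strongest counter-argument is the study boundary. Open-label drug is given under TNX-CY-P306, and SAP 3.2 lists only the two randomized treatments for this trial. On that reading, the last dose of study medication is the last blinded dose, and open-label data never enter these tables beyond the ten-day window. The reading is reasonable, but it does not help: the movers then bring only placebo-period data into the drug column, which is the dilution case computed above.

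Second, a table free of the reassignment is already planned. On the base case with no dropout, and with those ongoing averaging 6 weeks of follow-up, the Early Stop Safety Population holds 275 × 12/(275 × 12 + 76 × 6) = 3300/3756, or 88% of double-blind person-time. That lowers the stakes. It does not make the other required table right, and the full Safety Population remains the default.

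Third, the affected outputs are descriptive, SAP 8.3 repeats demographics for all randomized and for the mITT population, and the problem needs an early stop for success. All of this is true and limits the weight of the point.

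Fourth, SAP 7.1.1.2 is partly redacted, and the ISAP, the IDMC charter and the P306 protocol are not available, so a cut rule could exist there. The claim is confined to visible text for that reason. The population definition in SAP 6 is not redacted and would still need correcting.

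Finally, the completer overlap is conditional: SAP 3.4 gives no timing for entry to the extension. It remains a secondary ambiguity.

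**Conclusion.** The concern holds. The reassignment is explicit in SAP 6, and nothing visible limits its effect at the first open-label dose. Followed as written, the rule makes the full Safety Population table after an early stop for success an invalid double-blind comparison.

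Confidence is high on the text and low on the size. The ranges above are illustrations under assumed accrual, dropout, uptake and event risk; the error is present for any nonzero number of placebo rollovers. If only double-blind events count, a real drug excess is understated. If open-label events count too, it can be overstated. Efficacy, analyzed as randomized, is not affected.

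**What to change.** - **SAP 6:** delete the parenthesis on rolled-over participants, and classify the Safety Population by treatment actually received in the double-blind period.
- **SAP 10.1 and 11.2:** end double-blind safety data, including the ten-day window and exposure, at the first open-label dose, for early-stop rollovers and for completers who enter an extension. Apply the same cut to laboratory values, vital signs and C-SSRS.
- **Open-label events:** report them separately or in TNX-CY-P306, and say which.
- **Lead table after an early stop:** use the full double-blind Safety Population so defined, with the Early Stop Safety Population as supportive.
- **Protocol 13.1:** align the sentence on the highest dose issued.
- **SAP 4.2 (wording only):** say that the restriction to the early stop efficacy population covers efficacy analyses.

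The cost is a few sentences in the SAP and one data-cut flag in the datasets, with no new data collection. The Protocol 13.1 sentence would need EC/IRB approval under Protocol 14.1. Because Protocol 13.1 refers to the SAP for detail, the core correction does not depend on it.
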